9.2 Primary Endpoint(s)

9.2.1 Primary Variable(s) Analysis

The primary efficacy analysis will be based on the ITT analysis set. The proportion of subjects in remission, defined as rectal bleeding of 0 and stool frequency scores of 0 or 1 with an endoscopic score of 0 or 1 in the Clinical and Endoscopic Response Score at Month 6, will be assessed by the Mantel-Haenszel test stratified by the randomization strata at a two-sided 0.05 significance level. Subjects who discontinue the double-blind regimen before Month 6, as well as subjects with missing remission assessment at Month 6, will be considered not having met the remission criteria. The common odds ratio will be estimated using the Mantel-Haenszel adjusted odds ratio estimate, and its 95% confidence interval will be provided. The homogeneity of odds ratios across the randomization strata will be tested by the Breslow-Day test at a 0.05 significance level, and the odds ratio for each stratum will be presented in forest plots. The quantitative or qualitative nature of the possible treatment by stratum interaction will be assessed and discussed.

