4.3.2 Prohibited Therapy

The following medications are prohibited during the trial: 5-ASA products (oral or topical rectal), loperamide and other antidiarrheal agents, mucilages, antibiotics (metronidazole and ciprofloxacin), NSAIDs, nicotine patch, corticosteroids (oral, intravenous, intramuscular, or rectal), immunomodulating/suppressing drugs and biologics. Aspirin (except for cardioprotective reasons - maximum dose 325 mg/day) is prohibited during the trial.

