4.4 Withdrawal Criteria

Subjects have the right to withdraw from the trial at any time for any reason, without the need to justify their decision. However, the investigator should record the reason for the subject's withdrawal. The investigator also has the right to withdraw subjects.

Subjects will be withdrawn in the following cases:

- pregnancy at any time during the trial will be a reason for withdrawal
- withdrawal of consent
- worsening of UC with a need for an escalation of the therapy (i.e., surgical therapy, use of steroids, immunosuppressive or immunomodulating drugs, biologics, increase dose of 5-ASA in any form)
- request for termination of the trial by regulatory authorities or sponsor
- the subject develops any AE that, in the opinion of the investigator, warrants the subject's withdrawal from treatment. An AE form will be completed as appropriate, and the subject will be followed until the event is clinically stable.

For subjects who discontinue due to an AE, all efforts will be made to follow the outcome of the AE and to assess the efficacy criteria.

For any discontinuation, the investigator will obtain all the required details and document the date of the premature termination and the main reason in the electronic case report form (eCRF). Since an excessive rate of withdrawals can render the trial devoid of meaning, the unnecessary withdrawal of subjects should be avoided.

Subjects who withdrew from the trial will not be replaced.

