3.2 Determination of Sample Size

The true remission rates at Month 6 for mesalamine 2 g extended release granules (sachet) and placebo regimens were assumed as 68% and 49%, respectively, based on The mesalamine Study Group (1996)(3), Hawkey et al (1997)(4), and Apriso™ package insert (2009)(5). Under these assumptions, a sample size of 120 randomized subjects per group will provide at least 85% power to detect a statistically significant treatment group difference in the remission rate at a two-sided 0.05 significance level using the chi-square test. To maintain the power for the primary efficacy analysis that excludes subjects who are rolled over from the placebo group in the 000174 trial via Pathway 1, approximately 260 subjects will be randomized.

4 Subject Disposition

The number of screened subjects will be summarized, and for subjects not randomized, the primary reason for exclusion from randomization will be summarized.

The number and percentage of subjects who are randomized, are treated with IMP, prematurely discontinued, and completed the trial will be summarized with the reason of premature discontinuations.

The time to discontinuation will be summarized by the Kaplan-Meier estimates, and the treatment group difference will be tested by the log-rank test. In addition, reason-specific discontinuation will be summarized by the cumulative incidence estimates.

5 Protocol Deviations

The following protocol deviations will be identified as major protocol deviations:

- Overall IMP compliance of less than 80%
- Not taking the randomized IMP
- Taking prohibited medications

The final definition of major protocol deviations will be determined prior to breaking the blind.

The number and percentage of subjects with protocol deviations will be summarized.

6 Analysis sets

For each analysis set, the number and percentage of subjects excluded from it will be summarized by the reason of the exclusion.

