6.2 Intention-To-Treat Analysis Set

The intention-to-treat (ITT) analysis set includes all randomized subjects who were assigned to mesalamine 4 g extended release granules in the 000174 trial or randomized via Pathways 2 or 3. Analyses for the ITT analysis set will be conducted according to the randomized treatment regardless of the actual treatment received.

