6.4 Per Protocol Analysis Set

The Per-protocol (PP) analysis set includes all subjects who receive at least one dose of IMP and who do not have any of the major protocol deviations defined in Section 5 in the ITT analysis set.

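### The primary non-remission rule misses subjects who take a prohibited UC-active drug without being withdrawn

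*SAP*

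**What the plan says.** The primary analysis uses the ITT set. SAP 9.2.1 assigns non-remission by rule to "Subjects who discontinue the double-blind regimen before Month 6, as well as subjects with missing remission assessment at Month 6", and protocol 9.6.2 matches it. Everyone else is scored on the observed Month 6 bleeding, stool frequency and centrally read endoscopy results.

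Three other parts of the plan bear on this:

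- **Withdrawal.** Protocol 4.4 states "Subjects will be withdrawn in the following cases" and includes "worsening of UC with a need for an escalation of the therapy (i.e., surgical therapy, use of steroids". The list continues with immunosuppressive or immunomodulating drugs, biologics and "increase dose of 5-ASA in any form". Protocol 3.5.7 gives the same trigger.
- **Prohibited drugs.** Protocol 4.3.2 begins "The following medications are prohibited during the trial: 5-ASA products (oral or topical rectal" and goes on to corticosteroids, immunomodulating or suppressing drugs and biologics. It also lists drugs that are not UC therapy in this sense, such as antidiarrheals, NSAIDs and two antibiotics. It attaches no withdrawal or endpoint consequence.
- **Deviations.** SAP section 5 lists "Taking prohibited medications" as a major deviation. SAP 6.4 limits the per-protocol set to treated subjects "who do not have any of the major protocol deviations defined in Section 5 in the ITT analysis set".

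**The concern.** The primary objective is to show that the randomized 2 g mesalamine regimen maintains remission better than placebo. A remission reached with added 5-ASA or a steroid does not answer that question. The plan appears to share this view, because its time-to-relapse endpoint treats withdrawal for escalation with these same drug classes as relapse.

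The non-remission rule, however, works through withdrawal and not through the drug taken. A subject may take a UC-active drug without meeting the withdrawal trigger, or may meet it and not be withdrawn. Examples are 5-ASA taken on the subject's own initiative, a steroid for another condition, or a withdrawal rule that was not applied. Such subjects fall outside both limbs of the rule. If they are unevenly spread between the arms, the odds ratio is distorted.

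**Working it through.** **Tracing one subject through the rules.**

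1. Worsening UC, escalated, withdrawn before Month 6: discontinued, so non-remitter under SAP 9.2.1. This main case is handled.
2. Prohibited UC-active drug taken, study drug stopped before Month 6 for any reason: also a non-remitter.
3. Prohibited UC-active drug taken, study drug continued, Month 6 scores missing: non-remitter.
4. Prohibited UC-active drug taken, study drug continued, Month 6 criteria met: neither limb applies, so remitter.

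Only case 4 is open. No sensitivity analysis in SAP 9.2.2 scores it as failure. The per-protocol analysis removes the subject. The multiple-imputation and pattern-mixture analyses replace missing scores, and these scores are present. The last-observed-score analysis has no exclusion for scores taken after such a drug.

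**Reproducing the plan's power.** Inputs from SAP 3.2: p1 = 0.68, p2 = 0.49, n = 120 per group, two-sided alpha 0.05, chi-square test. With pooled variance under the null, no continuity correction and pbar = (p1 + p2)/2:

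z = [ (p1 − p2) − 1.96 × √(2 × pbar × (1 − pbar)/n) ] / √( (p1(1 − p1) + p2(1 − p2))/n )

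- pbar = 0.585; null SE = √(2 × 0.585 × 0.415/120) = 0.0636; 1.96 × 0.0636 = 0.1247
- alternative SE = √((0.2176 + 0.2499)/120) = 0.0624
- z = (0.19 − 0.1247)/0.0624 = 1.05, so power = 85.2%

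This agrees with the stated figure of at least 85%.

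**Assumed case-4 rates.** The documents give none. Each row adds the stated percentage points of case-4 remitters to the planning rates and assumes that each would otherwise have been a non-remitter.

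| Added points, mesalamine / placebo | Rates | Difference (points) | Odds ratio | Power, 120 per arm |
|---|---|---|---|---|
| 0 / 0 | 68% v 49% | 19 | 2.21 | 85.2% |
| 0 / 1 | 68% v 50% | 18 | 2.13 | 81.3% |
| 1 / 3 | 69% v 52% | 17 | 2.05 | 77.2% |
| 0 / 5 | 68% v 54% | 14 | 1.81 | 60.5% |
| 2 / 2 | 70% v 51% | 19 | 2.24 | 85.8% |
| 3 / 0 | 71% v 49% | 22 | 2.55 | 94.0% |

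Classing case-4 subjects as non-remitters returns every row to the first. For scale, 3% of 120 is 3.6, or about four subjects. The formula is for the unstratified test used in the sample-size section; the analysis itself is stratified.

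**The case against.** The strongest reply is that withdrawal already closes the gap. Protocol 4.4 names essentially the drug classes at issue, so a subject whose UC worsens and is escalated should be withdrawn and counted as a failure. This stands for the main case. A reader might infer that any subject in remission at Month 6 because of steroids or extra 5-ASA counts as a success; the documents do not support that. What remains is use outside the trigger, or a trigger not acted on.

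A reader might also infer that listing prohibited medication as a major deviation shows that the plan expects users to stay in, and so contradicts the withdrawal rule. It does not. A subject who took a steroid and was withdrawn has the same deviation, and the category also covers many drugs that are not UC treatments.

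It can be said that scoring these subjects as observed is a deliberate choice, since SAP 6.2 states: "Analyses for the ITT analysis set will be conducted according to the randomized treatment regardless of the actual treatment received". That sentence settles the arm in which a subject is analysed. It does not address added UC drugs. Using the observed outcome would be a legitimate strategy if stated, but the plan does not state it.

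The per-protocol analysis is a partial check, because it removes the doubtful successes. It does so by excluding subjects after randomization, which answers a different question from counting them as failures.

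Finally, if use is commoner on placebo the effect is diluted, which costs power and does not produce a false positive. That is plausible, but nothing in the documents establishes the direction.

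**Conclusion.** The point holds as a minor gap. The primary rule depends on withdrawal to turn added UC therapy into non-remission, and it leaves subjects who are not withdrawn to be scored on their observed Month 6 result. The number is probably small: each must take a UC-active drug, avoid withdrawal and still meet all three remission components.

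The size cannot be fixed from the documents. Over the assumed rates above, power runs from 60.5% (5 extra points on placebo only) to 94.0% (3 extra points on mesalamine only), and equal use of 2 points in each arm leaves it at 85.8%. Use that is commoner on placebo dilutes the effect; use that is commoner on mesalamine inflates it. A claim that the bias must run toward no effect would go beyond the evidence. The case for the change does not depend on direction: how these subjects are classified in the primary endpoint should be written down before unblinding.

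**What to change.** Add to SAP 9.2.1 that subjects who take a prohibited UC-active medication after randomization and before the Month 6 assessment are classed as non-remitters, whether or not they were withdrawn. Define the list as 5-ASA other than study drug, corticosteroids, immunomodulating or suppressing drugs, and biologics. Put the matching rule in SAP 9.3 for the generalized estimating equations analysis of clinical remission, applied to assessments after the drug was taken.

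Identify the subjects from the concomitant medication log by blinded review before unblinding. Concomitant medication is collected at every visit, and analysis sets must in any case be finalized before the blind is broken, so little extra work is needed. SAP section 12 now declares no deviation from the protocol analysis. It should record this change, and the rule in the protocol synopsis and protocol 9.6.2 should be reconciled with it.

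The costs are slightly lower remission rates and some bluntness: a steroid course for an unrelated condition would also count as failure. The change concerns endpoint classification only and leaves treatment, withdrawal and other clinical management as they are.

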9.2.2 Sensitivity Analyses

The following sensitivity analyses will be conducted to assess the robustness of the primary analysis:

- As-treated analysis based on actually received treatment
- Analysis on the all randomized analysis set
- Analysis on the mITT analysis set
- Analysis on the PP analysis set
- Analysis using the last observed Clinical and Endoscopic Response Score

The same analysis conducted for the primary analysis will be repeated for these sensitivity analyses.

Since the definition of remission was modified during the study, an analysis based on the original definition, i.e., rectal bleeding and stool frequency scores of 0 with an endoscopic score of 0 or 1 in the Clinical and Endoscopic Response Score, will also be conducted for reporting purpose.

In addition, sensitivity analyses using multiple imputation (MI) methods and pattern mixture models (PMMs) under missing at random (MAR) and missing not at random (MNAR) assumptions, respectively, will be conducted.

Under the MAR assumption, the missing stool frequency and rectal bleeding scores (Clinical Response scores) for Months 2, 4, and 6 will be imputed sequentially by regression-based imputation models using treatment group, baseline characteristics, and outcomes from preceding visits as the predictors. Once the missing Month 6 Clinical Response scores have been imputed, Month 6 Endoscopic Response score will be imputed by regression-based imputation models using treatment group, baseline characteristics, and Month 6 Clinical Response scores as the predictors. Based on the imputed Clinical and Endoscopic Response scores, the remission status at Month 6 will be determined. This imputation procedure will be repeated 100 times, and the primary analysis method will be applied to each of the imputed dataset. A combined estimate of the odds ratio for the treatment group compared to the control group and its 95% confidence interval will be obtained by the methods described in Rubin (1987)(6) .

Under the MNAR assumption, a similar MI method described above will be applied. However, in this analysis, only the data from the control group will be used for the regression-based imputation for Clinical Response scores at each visit and Endoscopic Response score at Month 6 by assuming that subjects from the treatment group will follow the same profile as the subjects on the control group after withdrawal from the study (Little & Yau, 1996(7); Ratitch & O’Kelly, 2011(8)).

The primary endpoint will also be analyzed for the following subgroups for the ITT analysis set using the same method as the primary efficacy analysis. The homogeneity of odds ratios across the strata will be tested by the Breslow-Day test at a 0.05 significance level, and the odds ratios for each subgroup will be presented in forest plots.

- Baseline demographic characteristics (age, gender, and race)
- Geographical region (North America including US and Canada or rest of the world)

The treatment group comparisons after controlling the randomization strata and each factor listed above will be conducted by the Mantel-Haenszel test as sensitivity analyses.

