9.1 General Considerations

All statistical tests will be conducted at a two-sided 0.05 significance level.

All secondary endpoints will be tested without adjustment for multiplicity.

Randomization strata will be included in stratified analyses for efficacy endpoints. For the ITT, mITT, and PP analysis sets, randomization strata will be defined as follows:

- Stratum 1: Pathway 1 (mesalamine 4 g extended release granules arm in the 000174 trial)
- Stratum 2: Pathway 2
- Stratum 3: Pathway 3

Randomization strata for the all randomized analysis set will be defined as follows:

- Stratum 1: Pathway 1a (placebo arm in the 000174 trial)
- Stratum 2: Pathway 1b (mesalamine 4 g extended release granules arm in the 000174 trial)
- Stratum 3: Pathway 2
- Stratum 4: Pathway 3

Stool frequency and rectal bleeding scores at each visit will be calculated as an average of the daily scores collected within 5 days prior to the visit (excluding the visit day and the day before the visit day if the bowel preparation is needed on the day before the visit). If the daily scores in this period are available for fewer than 3 days, the average score will be considered missing. The average scores will be rounded to the nearest integer for the final score determination (e.g., 0.3 will be rounded to 0, and 0.5 will be rounded to 1). Handling of missing data in the statistical analyses will be described for each endpoint.

For the endoscopic assessment, the outcomes determined by the independent central reading procedure will be used for all analyses.

For visit-based data, the data collected on the day that is closest to the scheduled trial day within a window will be assigned to the corresponding analysis visit. [Table 2](#) shows the scheduled trial day and window for each analysis visit.

Table 2 Scheduled trial day and window for analysis visits

Analysis visit	Scheduled trial day	Window
Baseline	Day 1	prior to the first dose of IMP

Analysis visit	Scheduled trial day	Window
Week 2	Day 14	Day 1 to Day 35
Month 2	Day 56	Day 36 to Day 84
Month 4	Day 112	Day 85 to Day 140
Month 6	Day 168	Day 141 or after

If the closest day cannot be uniquely identified for an analysis visit, the data collected on an earlier trial day will be assigned to the analysis visit.

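### The two imputation-based sensitivity analyses in SAP 9.2.2 make no exception for subjects withdrawn for UC escalation, so a documented relapse before Day 141 can be drawn as a Month 6 remission

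*SAP*

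**What the plan says.** **Relapse and the primary rule.** Protocol 4.4 makes UC worsening that needs escalated therapy a ground for withdrawal, and has the main reason for any discontinuation entered in the eCRF. SAP 9.3 takes the day of that withdrawal as the relapse event. In SAP 9.2.1, "Subjects who discontinue the double-blind regimen before Month 6, as well as subjects with missing remission assessment at Month 6" count as not in remission.

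**MAR analysis (SAP 9.2.2).** The "missing stool frequency and rectal bleeding scores (Clinical Response scores) for Months 2, 4, and 6 will be imputed sequentially", using arm, baseline variables and results from earlier visits. Month 6 endoscopy is then imputed from arm, baseline variables and the Month 6 clinical scores. Remission is derived from the completed scores, 100 times. The output is "A combined estimate of the odds ratio for the treatment group compared to the control group" with its 95% confidence interval.

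**Control-based analysis (SAP 9.2.2).** The method is similar, but the models are fitted to control data only, on the assumption that "subjects from the treatment group will follow the same profile as the subjects on the control group after withdrawal from the study".

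**Timing.** The Month 6 window in SAP 9.1 is "Day 141 or after". Within a window, "the data collected on the day that is closest to the scheduled trial day within a window will be assigned to the corresponding analysis visit". Protocol 3.5.8 plans no follow-up once participation ends. Protocol 6.1 (note to Table 1) and 7.1.2 require end-of-treatment assessments, including endoscopy, at early withdrawal.

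**The concern.** Imputation is meant for outcomes that nobody knows. A subject withdrawn because the disease flared and therapy had to be stepped up has a recorded outcome: the trial's own relapse event. SAP 9.2.2 treats that subject like one who moved away while well. Both lack a Month 6 score, and both receive one from a model that is not told why they left.

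What is at stake is the meaning of the robustness check. If its odds ratio differs from the primary one, the reader cannot tell whether the cause is uncertainty about unknown outcomes or the partial relabelling of known relapses.

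**Working it through.** **1. The plan's own figures.** Inputs from SAP 3.2: remission 68% vs 49%, 120 per group, two-sided 0.05, chi-square test.
- Pooled SE = √(2 × 0.585 × 0.415 / 120) = 0.0636. Unpooled SE = √((0.68 × 0.32 + 0.49 × 0.51) / 120) = 0.0624.
- Power = Φ((0.19 − 1.96 × 0.0636) / 0.0624) ≈ 85.2%, which agrees with the stated minimum of 85%.
- Planned difference 19.0 points; odds ratio (0.68/0.32) / (0.49/0.51) = 2.21.

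**2. Who is imputed.** After an escalation withdrawal before Day 141 there is no further follow-up, so no score falls in the Month 6 window and it is imputed. A withdrawal visit on Day 141 or later falls in that window and is not imputed if its scores are usable.

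**3. How much of the flare reaches the models.**
- The early-withdrawal endoscopy is not a listed predictor in any model.
- The withdrawal-visit clinical score can enter as an earlier-visit result, but the closest-day rule drops it when an on-time visit already fills the window. With visits on Days 14, 56 and 112, it is dropped on Days 15–35 (21), 57–84 (28) and 113–140 (28): 77 of 140 days (55%).
- That count uses a Week 2 score, which Protocol 7.1.3 provides for. SAP 3 mentions clinical scores only at Months 2 and 4; without Week 2 the count is 35 + 28 + 28 = 91 (65%).
- Over all permitted visit windows the ranges are 64–77 and 81–91 days. These are calendar days, not a share of withdrawals.

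**4. Illustration.** The documents give no withdrawal rates, so these are assumptions. A share s of primary-analysis non-remitters are escalation withdrawals before Day 141, and nothing else is missing. Each is drawn in remission at k times the rate of non-withdrawn subjects in the reference arm (own arm for MAR, placebo for control-based), with k = 0.5 or 1.
- Withdrawn: wA = 0.32s, wP = 0.51s. Rate in the rest: qA = 0.68/(1 − wA), qP = 0.49/(1 − wP).
- MAR: 0.68 + wA·k·qA vs 0.49 + wP·k·qP.
- Control-based: 0.68 + wA·k·qP vs 0.49 + wP·k·qP.

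At s = 0.50: wA = 0.16, wP = 0.255, qA = 0.8095, qP = 0.6577.

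| Analysis | k | Mesalamine | Placebo | Difference (points) | OR |
|---|---|---|---|---|---|
| Planned | – | 68% | 49% | 19.0 | 2.21 |
| Control-based | 0.5 | 73.26% | 57.39% | 15.9 | 2.03 |
| Control-based | 1 | 78.52% | 65.77% | 12.8 | 1.90 |
| MAR | 0.5 | 74.48% | 57.39% | 17.1 | 2.17 |
| MAR | 1 | 80.95% | 65.77% | 15.2 | 2.21 |

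Other shares:
- s = 0.25: control-based OR 2.13 to 2.06, MAR 2.20 to 2.21.
- s = 0.75: control-based OR 1.93 to 1.75, MAR 2.07 to 2.21.

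The unchanged MAR odds ratio at k = 1 is algebra. The odds become 0.68/(0.32(1 − s)) and 0.49/(0.51(1 − s)), and a common s cancels.

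**5. Direction.** With 10% escalation withdrawals in each arm, qA = 0.68/0.90 = 0.7556 and qP = 0.49/0.90 = 0.5444. The MAR OR becomes 2.37 (k = 0.5) or 2.59 (k = 1). The control-based OR becomes 2.25 or 2.31, with the difference still 19.0 points.

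**The case against.** **The analyses may deliberately ask a different question.** The primary analysis already uses the composite rule. MAR and control-based imputation ask what Month 6 would have looked like under a model, and some attenuation is intended in the control-based version. This is the strongest objection, and part of it stands: the SAP does not contradict itself here, and calling the results biased presumes that the composite rule is the target. But SAP 9.2.2 presents these analyses as tests of the primary result's robustness, and Protocol 9.6.2 ties them to remission assessments that are missing. A recorded relapse is a poor fit to that purpose, and all other missing outcomes would still be imputed.

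**The primary method is applied to each imputed dataset.** One could read this as restoring the non-remission rule. That rule already fails every missing Month 6 assessment, so imputation would then change nothing.

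**Relapse is visible elsewhere.** It is: in the primary analysis, in time to relapse, and in reason-specific cumulative incidence of discontinuation. No success criterion depends on the two analyses. This limits the weight of the point.

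**The figures rest on assumptions.** They do. The case in which the check looks stronger than the primary result needs equal escalation in both arms beside a 19-point remission effect, which is strained. Its largest value also needs the flare to have no influence on the draw.

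**A further reading goes too far.** A reader might infer that "Analysis using the last observed Clinical and Endoscopic Response Score" carries baseline remission forward for relapsers, since no post-baseline limit is stated and entry requires remission. The documents do not support treating this as a separate defect. The full assessment is required at early withdrawal, so relapsers should normally have a post-baseline score. In addition, "The same analysis conducted for the primary analysis will be repeated for these sensitivity analyses" can be read as failing anyone without one.

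**Conclusion.** The point holds as a gap in two supplementary analyses. As written, both can turn some documented relapses before Day 141 into Month 6 remissions, and neither uses the early-withdrawal endoscopy.

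A reader might go further and infer that all relapses are reclassified, or that the trial's main conclusion is at risk. Neither follows. Earlier-visit scores can carry flare information into the draw, so reclassification is partial, and the primary, all-randomized, mITT and PP analyses keep the non-remission rule.

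Size and direction cannot be fixed from the documents. If placebo has more escalation withdrawals, the control-based odds ratio falls (2.03 to 1.90 in the middle case, 2.13 to 1.75 across the shares tried). The MAR odds ratio moves little, although its risk difference shrinks. Another split between the arms could move the result the other way. Confidence is high on the reading of the text and low on the magnitude.

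**What to change.** In SAP 9.2.2, add that in the multiple-imputation and pattern-mixture analyses, subjects whose eCRF withdrawal reason is UC worsening or escalation are held as not in remission in all 100 imputed datasets, and that only the other missing Month 6 assessments are imputed. Settle this before the blind is broken.

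The cost is a sentence in the SAP and one programming flag from a field already collected. There are two downsides. The rule depends on correct coding of the withdrawal reason, and it moves both analyses closer to the primary rule, so they add less as separate checks.

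Stating that the last-observed analysis uses post-baseline scores only would be a harmless wording clarification, no more.
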